2.8.1.1 Adverse events of special interest (AESI)/ grouping of AEs

For each specified AESI, the number and percentage of patients with at least one event of the AESI occurring during the on-treatment period will be summarized. Summaries of these AESIs will be provided grouped by CTCAE grades, SAE, relationship, leading to treatment discontinuation, leading to dose adjustment/interruption, etc.

Such groups consist of adverse events for which there is a specific clinical interest in connection with everolimus treatment (i.e., where everolimus may influence a common mechanism of action responsible for triggering them), or adverse events which are similar in nature (although not identical). A non-exhaustive list of AE groupings includes “Stomatitis and related events”, “Infections”, “Amenorrheas” and “Non-infectious pneumonitis”. All notable adverse event groupings are defined through the use of Standardized MedDRA Queries (SMQ), Preferred Terms (PT), High Level Terms (HLT), or System Organ Classes (SOC), or through a combination of these four components. At the project level, a SAS dataset named eCRS contains the exact composition of the adverse events groupings will be used to map reported adverse events to the notable adverse events groupings. This dataset may be updated (i.e., it is a living document) based on review of accumulating trial data, and it is the most up to date version at the time of DB lock that will be used. Note that certain adverse events may be reported within multiple groupings.

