1.2.3 Clinical experience of everolimus

Clinical Safety, Tolerability and Efficacy

Phase III study CRAD001M2302 in renal angiomyolipoma associated with TSC (EXIST-2)

A total of 118 patients with renal angiomyolipoma associated with TSC were enrolled to this study between 2009 and 2014 (01-Apr-2014 cut-off). 79 were initially treated with everolimus and 39 with placebo. Upon disease progression or study unblinding, patients were allowed to crossover from placebo to everolimus. A total of 112 patients were treated with at least 1 dose of everolimus. The data described below represent the cumulative experience of 112 patients treated with everolimus at the time of the final treatment cut-off date, 04-Feb-2015.

Efficacy

At the primary analysis cut-off date (30-Jun-2011), the angiomyolipoma response rate was statistically significantly higher in the everolimus arm compared to the placebo arm (33/79 patients, 41.8% vs 0/39 patients, 0.0%; $p < 0.0001$). Cumulative experience for angiomyolipoma response at the final cut-off date (04-Feb-2015) demonstrated that the tumors in 65/112 patients had responded to treatment (response rate = 58.0%; 95% CI: 48.3, 67.3). The percentage of patients achieving $\geq 30\%$ reduction in angiomyolipoma volume was sustained while the degree of reduction ($\geq 50\%$ volume reduction and median percentage reduction) improved over the course of the study:

- 78/104 patients (75%) experienced reductions of $\geq 30\%$ at Week 12, 79/98 patients (80.6%) at Week 96, and 52/61 patients (85.2%) at Week 192;
- 46/104 patients (44.2%) experienced reductions of $\geq 50\%$ at Week 12, 62/98 patients (63.3%) at Week 96, and 42/61 patients (68.9%) at Week 192;
- The median percentage reduction in angiomyolipoma volume at Week 12, 96 and 192 was 46.4%, 58.9% and 61.9%, respectively.

The efficacy results confirmed that everolimus treatment effects in patients with TSC-associated angiomyolipoma were sustained over a period of time.

Everolimus was associated with a clinically relevant SEGA response rate of 48.0% ($n=24/50$, 95% CI: 33.7, 62.6).

The overall skin lesion response rate was 68.2% (73/107 patients) with one patient reporting a confirmed complete clinical skin lesion response and no patients experiencing progressive disease as their best response. Of 73 patients who had a response of the skin lesions, the median time to skin lesion response was 8.41 months (95% CI: 5.59, 11.53).

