Results from the non-interventional follow-up phase indicate that clinically significant treatment effects were attenuated in the evaluable patients following everolimus discontinuation, as shown by an increase in the volume of angiomyolipoma lesions previously reduced in size as a result of everolimus treatment. While in some cases post-discontinuation growth plateaued following discontinuation of everolimus and while lesion volumes did not

return to pre-treatment values, profound reduction in volumes were no longer detectable in the majority of patients within approximately one year of everolimus discontinuation.

Safety

The most common AEs ($\geq 30\%$ of patients) regardless of study drug relationship were nasopharyngitis (44.6%), stomatitis (42.9%), hypercholesterolemia (35.7%), headache (33.0%), acne (32.1%), and urinary tract infection (31.3%). Stomatitis, which is a known identified risk of everolimus treatment, was the most frequently reported individual AE suspected by the Investigator to be study-drug related in everolimus-treated patients (42.0%).

Other frequently reported AEs ($\geq 20\%$ of patients) with suspected relationship to study drug included hypercholesterolemia (30.4%), acne (25.9%), aphthous stomatitis (21.4%), and nasopharyngitis (21.4%). Amenorrhea (n=18/71, 25.4%) was frequently reported in the female population at risk (10-55 years of age).

Ten patients (8.9%) discontinued study drug due to the AEs.

Phase II study RAD001MCN30T in renal angiomyolipoma associated with TSC

18 Chinese adult patients with TSC-AML were enrolled in this single site investigator initiated study. A preliminary analysis was done with cut-off date 10-Oct 2015 when 15 patients were enrolled and 13 patients had received 10 mg everolimus per day for 3 months. Out of the 13 patients with at least 3 months treatment, 4 patients met the primary endpoint, which was defined as 50% or more reduction of renal AML volume relative to baseline in the absence of new renal AML $>1\text{cm}$ and no renal AML-related bleeding of grade ≥ 2 . The mean volume decrease at 3 months and 6 months was 30.78% and 50.22%, respectively.

Mouth ulceration, nasopharyngitis, hypercholesterolemia and irregular menstruation in females were the most common adverse events of which only 2 events had a CTCAE grade of 3 in the first 3 months.

Clinical Pharmacodynamics

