5.1 Patient population

The study patient population consists of 40 male or female adult patients (18 years of age or older) who have been diagnosed with renal AML associated with TSC that do not require immediate surgery.

The investigator or designee must ensure that only patients who meet all the following inclusion and none of the exclusion criteria are offered treatment in the study. Patients enrolled in this study are not permitted to participate in additional parallel investigational drug studies.

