2.8 Safety analyses

The assessment of safety will be based mainly on the frequency of adverse events and on the number of laboratory values that fall outside of pre-determined ranges. Other safety data (e.g., vital signs and special tests) will be considered as appropriate.

All safety outputs will use the Safety Set.

The safety summary tables will include only assessments collected no later than 30 days after the date of last administration of everolimus. The safety summary listings will include all assessments, with those collected later than 30 days after date of last everolimus being flagged.

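### By default the Amenorrheas event-of-special-interest rate is a percentage of all treated patients, men included, so it understates incidence in the women who can have the event

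*SAP*

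**What the plan says.** **AESI rule.** SAP 2.8.1.1 specifies what is summarised: "For each specified AESI, the number and percentage of patients with at least one event of the AESI occurring during the on-treatment period". It then adds breakdowns by grade, seriousness, relationship, discontinuation and dose change. On the content of the groupings it says: "A non-exhaustive list of AE groupings includes “Stomatitis and related events”, “Infections”, “Amenorrheas” and “Non-infectious pneumonitis". The exact composition sits in a project-level dataset that the SAP does not reproduce.

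**Population.** SAP 2.8: "All safety outputs will use the Safety Set". SAP 2.2 defines that set as everyone who took at least one dose. Protocol 5.1 describes who they are: "The study patient population consists of 40 male or female adult patients (18 years of age or older", with no upper age limit. Protocol 10.4.1 has safety tables presented for all patients together. Neither document gives a sex-specific or at-risk denominator for any event.

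**Background figures.** Protocol 1.2.3, on the pivotal study CRAD001M2302, does use such a denominator: "Amenorrhea (n=18/71, 25.4%) was frequently reported in the female population at risk (10-55 years of age". The same section states: "A total of 112 patients were treated with at least 1 dose of everolimus". For the earlier Chinese study it reports that mouth ulceration, nasopharyngitis, hypercholesterolemia and "irregular menstruation in females were the most common adverse events".

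**Related provisions.** SAP 2.2.1.1 repeats the main adverse event analyses by gender and by age below 65 against 65 and over, provided each class holds at least 10% of patients. SAP 2.4.1 counts exposed patients by gender and age. SAP 2.8.1 lists all adverse events and tabulates them by preferred term.

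**The concern.** Amenorrhea can occur only in women of reproductive age. A percentage of all treated patients is therefore not an incidence in anyone who could have the event. It depends on how many men happened to enrol as well as on the drug. The protocol's background section recognises this by using females at risk, and the SAP does not carry that practice over.

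The primary objective is to describe the incidence of adverse events in Chinese adults, and menstrual disturbance was already among the most common events in the earlier Chinese study. A reader of the AESI table would see a figure lower than the incidence in women at risk. The same dilution would run through the AESI breakdowns listed in SAP 2.8.1.1.

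**Working it through.** **Inputs.** From protocol 1.2.3: 18 women with amenorrhea among 71 females aged 10-55, and 112 everolimus-treated patients in all. From protocol 5.1: 40 patients of both sexes. The number of women in this study is not stated, so the at-risk share is an assumption shown as a range.

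**1. Reproduce the protocol's figure.** 18/71 = 0.2535, or 25.4%, as stated. The exact (Clopper-Pearson) 95% interval is 15.8% to 37.1%.

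**2. Apply the SAP's default denominator to the same count.** 18/112 = 16.1% (exact 95% interval 9.8% to 24.2%), assuming no events outside the 71. The factor is 71/112 = 0.63, and the difference is 25.4 - 16.1 = 9.3 percentage points. The neighbouring sentence in protocol 1.2.3 uses 20% of patients as its cut-off for frequently reported drug-related events. The event lies above 20% on one denominator and below it on the other.

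**3. Project to this study.** Suppose the true rate in women at risk is 25.4% and n of the 40 patients are at risk. The expected number of events is n x 18/71. The default percentage divides this by 40.

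| At risk, n (share) | Expected events | Out of 40 | Out of n |
|---|---|---|---|
| 20 (50%) | 5.07 | 12.7% | 25.4% |
| 24 (60%) | 6.08 | 15.2% | 25.4% |
| 28 (70%) | 7.10 | 17.7% | 25.4% |
| 32 (80%) | 8.11 | 20.3% | 25.4% |

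The pivotal study's own share, 71/112 = 63%, lies inside the assumed range.

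**4. Whole-number illustration.** With 24 women at risk and 6 events, the at-risk figure is 6/24 = 25.0% (exact 95% interval 9.8% to 46.7%). The default figure is 6/40 = 15.0% (5.7% to 29.8%). The intervals are wide and overlap, so this is a matter of what the point estimate describes and not of precision.

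**5. How far the existing provisions repair it.** The 10% condition in SAP 2.2.1.1 means at least 0.10 x 40 = 4 patients of each sex. If that is met and the preferred-term tables count as main analyses, amenorrhea as a single term would appear with women as denominator. Two gaps remain. The SAP does not define which tables are main analyses, so it is unclear whether the AESI groupings are repeated. Also, the only age split is at 65, so a female column still includes any women past reproductive age.

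**The case against.** The strongest reply is that no information is lost. The gender repeat is meant to find safety problems confined to a subgroup, and on an ordinary reading it covers the preferred-term tables. Exposed patients are counted by gender, and all adverse events are listed. Since only women can have the event, anyone can divide the AESI count by the number of women. This stands, and it is why the point is minor. A reader might infer that a female rate cannot be obtained from the report, and the documents do not support that. The division still gives all women and not women at risk, because SAP 2.4.1 names no age bands, and it leaves the reader to correct a printed percentage.

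A second reply is that the all-patient denominator is inferred. Naming the Safety Set as the population does not forbid a female N for one row. That is fair: the rule comes from general statements and not from a sentence about amenorrhea. But it is what a programmer would follow by default.

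A third reply concerns the comparison with 25.4%. A reader might infer that a lower figure here would differ from the pivotal one through its denominator alone. The documents do not support that either. The pivotal figure belongs to cumulative data with a median follow-up of 47.2 months (protocol 1.1). Here treatment lasts at most 48 weeks, or 336/30.4375 = 11.0 months, plus 30 days of adverse event follow-up. The pivotal figure is also for amenorrhea as an individual event, in a paragraph on suspected drug-related events, whereas the SAP's Amenorrheas is a grouping that may hold more terms. Correcting the denominator would not by itself make the two rates comparable.

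**Conclusion.** The point holds as a reporting defect of limited reach. Read as written, the SAP prints a percentage for a named AESI grouping that understates incidence in those who can have it. The printed value is the at-risk rate multiplied by the at-risk share of the 40 patients. With a true rate of 25.4% and an assumed share of 50% to 80%, that gives 12.7% to 20.3%. Both the rate and the share are assumptions about this trial: the rate is borrowed from the pivotal study only to show scale, and the documents do not give the number of women.

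It would go too far to say that the primary endpoint is compromised. That endpoint is the overall incidence of adverse events and laboratory abnormalities, Amenorrheas is one example in an open list, and there is no hypothesis test. No decision named in the documents turns on this percentage. Priority: minor, a cheap improvement.

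**What to change.** In SAP 2.8.1.1:

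- State that percentages for the Amenorrheas grouping, and for other female reproductive terms, use female Safety Set patients at risk as denominator, with that N shown in the table. Ages 18-55 would serve, being the adult part of the 10-55 range in protocol 1.2.3. Age is only a proxy for being at risk, so the definition should be printed with the table.
- Keep the all-patient percentage alongside if a uniform layout is wanted.
- State that the AESI tables are included in the gender repeat of SAP 2.2.1.1.
- Do not present the new denominator as making the rate directly comparable with CRAD001M2302. If 18/71 is cited next to it, add a footnote that the pivotal figure is cumulative over a much longer follow-up and refers to a single event.

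The cost is one or two sentences in the SAP and one extra denominator in programming. Age and sex are already collected (protocol 7.1.2.3), so no new data are needed. The downside for the sponsor is a higher stated incidence for this row.

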2.8.2 Deaths

Separate summaries for on-treatment and all deaths (including post-treatment death) will be produced by system organ class and preferred term.

All deaths will be listed for the safety set, post treatment deaths will be flagged. A separate listing of deaths prior to starting treatment will be provided for all screened subjects.

2.8.3 Laboratory data

The laboratory assessments include hematology, biochemistry, coagulation, urinalysis, hepatitis markers, and pregnancy test. Data from all sources (central and local laboratories) will be listed, but summary tables will only include data from the central laboratory (except urinalysis, where most assessments were done in local lab).

The frequency of notable laboratory abnormalities will be displayed by parameter.

The following summaries will be produced for laboratory data (by laboratory parameter – except for coagulation parameters):

- Number and percentage of patients with worst post-baseline CTC grade (regardless of the baseline status). Each patient will be counted only for the worst grade observed post-baseline.
- Shift tables using CTC grades to compare baseline to the worst post-baseline value will be produced for hematology and biochemistry laboratory parameters with CTC grades.
- For laboratory parameters where CTC grades are not defined, shift tables to the worst post-baseline value will be produced using the low/normal/high classifications based on laboratory reference ranges.

Note: As a project standard, shift tables using the low/normal/high classifications based on laboratory reference ranges to compare baseline to the final on-treatment laboratory value will not be produced.

The following listings will be produced for laboratory data:

- Listing of patients with laboratory values outside the laboratory reference ranges with values flagged to show the corresponding CTC grades and the classifications relative to the laboratory reference ranges.
- Listing of all laboratory data with values flagged to show the corresponding CTC grades and the classifications relative to the laboratory reference ranges.

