7.2.2.5 Laboratory evaluations

Clinical laboratory analyses (hematology, chemistry, coagulation, hepatitis markers, serum pregnancy) are to be performed centrally according to the schedule of assessments and collection plan outlined in [Table 7-1](#) and [Table 7-5](#). Details on the collection, shipment of samples and reporting of results by the central laboratory are provided to investigators in the Central Laboratory Manual/Flowchart. The urinalysis will only be performed by the local laboratory using dipstick analysis.

If at any time a patient has laboratory parameters obtained from a different (outside) laboratory, Novartis must be provided with a copy of the certification and a tabulation of the normal ranges and units for this laboratory. The investigator is responsible for reviewing all laboratory reports for patients in the study and evaluating any abnormalities for clinical significance.

For assessment of patients' eligibility to the study, only laboratory results from the central laboratory will be used (except in case of re-sampling and the results from the central laboratory are not yet available or are partial at Day 1, then eligibility may be based on the results from the local laboratory. In such case the results of the local laboratory will need to be recorded in the eCRF unplanned pages and a copy of the local lab normal ranges must be provided). Screening safety laboratory tests (hematology, biochemistry, lipid profile, urinalysis, and coagulation) will need to be repeated at Treatment Day 1 if they were collected more than 14 days prior to Treatment Day 1.

Unscheduled local laboratory assessments may be performed if medically indicated to document a (potential) AE or when the treating physician cannot wait for central laboratory results for decision making. In this particular situation, if possible, the blood sample obtained at the same time point should be submitted to the central laboratory for analysis in parallel

with local analysis. The results of the local laboratory will be recorded in the eCRF if any the following criteria are met:

- A treatment decision was made based on the local results, or
- There are no concomitant central results available, or
- Local lab results document an AE not reported by the central lab, or
- Local lab results document an AE where the severity is worse than the one reported by the central lab, or

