8.1 Adverse events

8.1.1 Definitions and reporting

An adverse event is defined as the appearance of (or worsening of any pre-existing) undesirable sign(s), symptom(s), or medical condition(s) that occur after patient's signed informed consent has been obtained.

Abnormal laboratory values or test results occurring after informed consent constitute adverse events only if they induce clinical signs or symptoms, are considered clinically significant, require therapy (e.g., hematologic abnormality that requires transfusion or hematological stem cell support), or require changes in study medication(s).

Adverse events that begin or worsen after informed consent should be recorded in the Adverse Events CRF. Conditions that were already present at the time of informed consent should be recorded in the Relevant Medical History page of the patient's CRF. Adverse event monitoring should be continued for at least 30 days following the last dose of study treatment. Adverse events (including lab abnormalities that constitute AEs) should be described using a diagnosis whenever possible, rather than individual underlying signs and symptoms. When a clear diagnosis cannot be identified, each sign or symptom should be reported as a separate Adverse Event.

Adverse events will be assessed and graded according to the Common Terminology Criteria for Adverse Events (CTCAE) version 4.03. Grade 1 to 5 will be used to characterize the severity of the Adverse Event.

If CTCAE grading does not exist for an adverse event, the severity of mild, moderate, severe, and life-threatening, death related to the AE corresponding respectively to Grades 1 - 5, will be used. Information about any deaths (related to an Adverse Event or not) will also be collected through a Death form.

The occurrence of adverse events should be sought by non-directive questioning of the patient (subject) during the screening process after signing informed consent and at each visit during the study. Adverse events also may be detected when they are volunteered by the patient (subject) during the screening process or between visits, or through physical examination, laboratory test, or other assessments. As far as possible, each adverse event should be evaluated to determine:

1. The severity grade (CTCAE Grade 1-5)
2. Its duration (start and end dates or ongoing at end of study)
3. Its relationship to the study treatment (reasonable possibility that AE is related: No, Yes)

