8.1.2 Laboratory test abnormalities

8.1.2.1 Definitions and reporting

Laboratory abnormalities that constitute an Adverse event in their own right (are considered clinically significant, induce clinical signs or symptoms, require concomitant therapy or require changes in study treatment), should be recorded on the Adverse Events CRF. Whenever possible, a diagnosis, rather than a symptom should be provided (e.g. anemia instead of low hemoglobin). Laboratory abnormalities that meet the criteria for Adverse Events should be followed until they have returned to normal or an adequate explanation of the abnormality is found. When an abnormal laboratory or test result corresponds to a sign/symptom of an already reported adverse event, it is not necessary to separately record the lab/test result as an additional event.

Laboratory abnormalities, that do not meet the definition of an adverse event, should not be reported as adverse events. A Grade 3 or 4 event (severe) as per CTCAE does not automatically indicate a SAE unless it meets the definition of serious as defined below and/or as per investigator's discretion. A dose hold or medication for the lab abnormality may be required by the protocol in which case the lab abnormality would still, by definition, be an adverse event and must be reported as such.

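### SAP 2.8.3 keeps local results out of the hematology and biochemistry summaries, so on the fixed Safety Set the count at worst grade ≥ k can be below, but never above, the count from all recorded values

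*SAP*

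**What the plan says.** SAP 2.5.1 names laboratory abnormalities beside adverse events as the primary endpoints. SAP 2.8.3 lists data from central and local laboratories alike, but for tabulation "summary tables will only include data from the central laboratory". The one exception is stated in brackets: "except urinalysis, where most assessments were done in local lab". The main laboratory table is by worst grade: "Each patient will be counted only for the worst grade observed post-baseline". Shift tables from baseline to the worst value follow the same source rule.

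Protocol 7.2.2.5 plans hematology and chemistry at the central laboratory. It allows unscheduled local tests when medically indicated or when a decision cannot wait, and gives five criteria for entering the local result in the eCRF. One is "There are no concomitant central results available", with no condition that the value be an AE. Others cover AEs that the central laboratory did not show, and the case "Local lab results document an AE where the severity is worse than the one reported by the central lab". A matching central sample is asked for, but only in these terms: "if possible, the blood sample obtained at the same time point should be submitted to the central laboratory for analysis in parallel".

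Protocol 8.1.1 says that abnormal laboratory values "constitute adverse events only if they induce clinical signs or symptoms, are considered clinically significant, require therapy", or require a change in study medication. Protocol 8.1.2.1 closes the other door: "Laboratory abnormalities, that do not meet the definition of an adverse event, should not be reported as adverse events".

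**The concern.** The protocol sets out to capture local results where the central laboratory has nothing or shows something milder. The SAP then leaves those results out of every hematology and biochemistry summary. A worst-grade table is sensitive to single values, and the planned central samples after Day 1 fall at Weeks 4, 12, 24 and 48 and at end of treatment. That leaves an interval of up to 24 weeks in which an unscheduled local sample may be the only observation.

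AE reporting covers part of this but is no substitute. Laboratory grades are assigned by program from observed values (protocol 10.4.3, SAP 5.3), whereas AE status depends on symptoms, clinical judgement, therapy or a drug change. AEs are also recorded by diagnosis where possible, so the AE tables do not reproduce laboratory grades. What is at stake is whether a reader of the summary tables can tell if local results would change any laboratory incidence. At present they cannot.

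**Working it through.** The plan gives no figure to reproduce: there is no hypothesis test, and the sample size is set by feasibility. The check is a comparison of rules, a short argument on maxima, and some arithmetic for scale.

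**Inputs.** Denominator: Safety Set (SAP 2.8), 40 patients treated (protocol, Amendment 2 rationale). Statistic: worst post-baseline CTC grade per patient (SAP 2.8.3). Source: central only, except urinalysis. The number of patients with a deciding local value is not given.

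**1. Where a recorded local hematology or biochemistry value ends up**

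| Local value | AE tables | Laboratory summary tables | Listings with CTC flags |
|---|---|---|---|
| Meets the AE definition | yes | no | yes |
| Does not meet it | no | no | yes |

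The second row will be mainly low grade. For example, protocol Table 6-4 calls for no dose change for platelets at grade 1 or neutrophils at grade 1 or 2. Such a value, without symptoms, therapy or a judgement of clinical significance, is not an AE.

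**2. Direction for grade ≥ k.** For patient i let C be the worst central grade, L the worst local grade, and A = max(C, L). Then A ≥ C, so every patient with C ≥ k also has A ≥ k. With 40 fixed in the denominator:

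all-source incidence − central-only incidence = m/40, where m = number of patients with C < k ≤ L (or with no central value and L ≥ k).

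Since m ≥ 0, the central-only figure cannot be the higher one. A local value at or below the patient's worst central grade adds nothing. A simulation of 5,000 data sets of 40 patients at four cut-offs (20,000 comparisons) gave 0 cases with central-only higher.

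**3. Where the direction fails**

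- *Exact-grade cells.* Assume worst central grades 0/1/2/3 in 34/3/2/1 patients, and one grade 2 patient with a local grade 3. Adding local data takes the grade 2 cell from 2/40 = 5.0% to 1/40 = 2.5%, and the grade 3 cell from 1/40 = 2.5% to 2/40 = 5.0%. Grade ≥ 2 stays at 3/40 = 7.5%; grade ≥ 3 rises from 2.5% to 5.0%.
- *Evaluable-only denominators.* If one patient has only a local grade 0 value and four others reach grade k centrally, central-only gives 4/39 = 10.26% and all-source gives 4/40 = 10.00%. In the same simulation, this denominator made central-only higher in 968 of 20,000 comparisons; that count depends on arbitrary inputs and shows only that reversal is possible.
- *Shift tables.* If a patient's baseline would come from a different source, cells can move either way.

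**4. Scale.** One patient is 1/40 = 2.5 points. Assuming no central case at grade ≥ k, with exact (Clopper-Pearson) 95% intervals for scale only, since the SAP plans none for laboratory grades:

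| m (assumed) | Incidence | 95% interval |
|---|---|---|
| 0 | 0/40 = 0% | 0 to 8.8% |
| 1 | 1/40 = 2.5% | 0.06 to 13.2% |
| 2 | 2/40 = 5.0% | 0.6 to 16.9% |

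**The case against.** The strongest reply is that this is an openly stated and conventional choice of source. The SAP gives no explicit reason, but the urinalysis exception implies one: each test is tabulated from the laboratory where it was planned. Protocol 9.3 also has safety laboratory data collected centrally. That stands, and central-only is a sound main display with one set of ranges.

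It also stands that the affected group is narrow. The value must be local, post-baseline and above everything the central laboratory found in that patient. The more serious values should meet the AE definition and reach the AE tables. All values are listed with grades, and listings for 40 patients can be read through. The planned table shows exact grades, so grade ≥ k has to be derived by adding cells, and the SAP does not say whether patients without a post-baseline central value stay in each parameter's denominator.

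Two further replies carry less weight. SAP 2.5.4 allows sensitivity analyses for missing assessments, but only if needed, so no planned summary results from it. And an all-source table would be built from selectively recorded results on mixed assays and ranges; where a parallel sample exists, taking the worse of two assays of one draw selects upward. That rules out replacing the central table. It does not rule out a labelled supplement.

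**Conclusion.** The point holds as an inexpensive improvement. For hematology and biochemistry, on a fixed denominator of 40, the central-only count at worst post-baseline grade ≥ k is equal to or below the count from all recorded values. The difference is 2.5 points per affected patient. The number affected is unknown and may be zero, and no test or decision threshold depends on it.

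A reader might infer that the plan understates laboratory toxicity throughout. The documents do not support that: they show a possible direction for one cumulative statistic, not a size, and single-grade cells can move either way. A reader might also infer that local results are lost, or that the SAP departs from the protocol without declaring it. Neither follows. The values are listed with their grades. Protocol 10.4.3 does not specify a laboratory source, and protocol 7.2.2.5 and 9.3 plan these tests centrally, so no entry in SAP section 4 is called for.

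**What to change.** Leave the central-only tables as the main display. Add to SAP 2.8.3 one supplementary table of worst post-baseline grade ≥ k by parameter, from central plus local on-treatment values, with all Safety Set patients in the denominator and local values graded under SAP 5.3. Give for each parameter the number of patients whose worst grade comes only from a local result. Keep the central baseline in the shift tables, with a footnote where only a local baseline exists.

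Label the table supplementary and say why: selective recording, mixed ranges, and upward selection where parallel samples exist. SAP 2.7.1 already describes what was seen at database lock, so if the table is added after lock, state that. If no patient is affected, one sentence saying so replaces the table.

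The cost is one paragraph and at most one table. The local values are already held and flagged, protocol 7.2.2.5 requires local normal ranges to be supplied, SAP 5.3 has a rule for local ranges that overlap a CTC grade, and local urinalysis results are already tabulated.
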